### **1.24 NCI CLINICAL DIRECTOR REPORTING**

Problems expeditiously reviewed by the OHSRP in the NIH eIRB system will also be reported to the NCI Clinical Director/designee; therefore, a separate submission for these reports is not necessary.

In addition to those reports, all deaths that occur within 30 days after receiving a research intervention should be reported via email unless they are due to progressive disease.

To report these deaths, please send an email describing the circumstances of the death to [[contact]](mailto:[contact]) within one business day of learning of the death.

## **1.25 NIH REQUIRED DATA AND SAFETY MONITORING PLAN**

### **1.25.1 Principal Investigator/Research Team**

The clinical research team will meet weekly when patients are being actively treated on the trial to discuss each patient. Decisions about dose level enrollment and dose escalation if applicable will be made based on the toxicity data from prior patients.

All data will be collected in a timely manner and reviewed by the principal investigator or a lead associate investigator. Events meeting requirements for expedited reporting as described in Section [7.2.1](#) will be submitted within the appropriate timelines.

The principal investigator will review adverse event and response data on each patient to ensure safety and data accuracy. The principal investigator will personally conduct or supervise the investigation and provide appropriate delegation of responsibilities to other members of the research staff.

## **STATISTICAL CONSIDERATIONS**

The primary objective of this exploratory trial is to obtain pilot data to assess the utility and role of mpMRI in localization and detection of focal prostate cancer both before and after treatment with pre-operative ADT and enzalutamide. Secondary objectives include obtaining pilot data to guide future studies with respect to determining genetic predictors and correlates of response to therapy as well as to link imaging information to genomic information related to resistance.

Patients who have newly diagnosed prostate cancer will undergo treatment with androgen deprivation therapy and enzalutamide and will undergo mpMRI imaging at screening and 6 months. The imaging will be used to monitor the changes in the individual tumors located within the prostate. As these patients will all have multiple tumors within the prostate, it is anticipated that approximately 25% of the patients will experience minimal declines in tumor and still have significant residual disease, 25% may have complete disappearance of tumor, and the remainder will show substantial improvement (disappearance of some lesions, with others being much smaller). To guide sample size determination, it is estimated that for an exploratory investigation of the association of genomic information and its relationship to response, it would be useful to have at least a minimum of 10 patients who still have significant residual disease in order to form preliminary assessments of the relationships noted. As such, if 50 total evaluable patients were to enroll on the trial and if the probability of being in this category was 25%, there would be 83.6% probability of having at least 10 such patients. Thus, this pilot study will plan to enroll 50 total evaluable patients who would all undergo primary treatment and mpMRI imaging to assess the role of imaging in this setting. The accrual ceiling will be 55 in order to accommodate a small number of patients who may be inevaluable. Successful use of this imaging will lead to analyses related to the association with genomic traits at baseline and prostatectomy and whether there is disappearance of tumor or not. On this trial, all of these investigations will be performed with exploratory, hypothesis generating intent.

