#### 1.1.2 Secondary Objectives

- To perform parallel sequencing of each unique tumor focus in the prostate before and after treatment with ADT and enzalutamide to determine the genetic predictors of primary resistance. (This will be done both inter-patient and intra-patient.)
- To determine the quantitative and qualitative mpMRI characteristics of response both before and after treatment, to predict resistance to intensive androgen targeted therapies and link imaging to genomic characterization of resistance.
- To evaluate the pathological complete response rate after neoadjuvant treatment with ADT and enzalutamide.

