### 1.2 BACKGROUND AND RATIONALE

It is expected that 29,480 men will die from prostate cancer in the US in 2014.[\[1\]](#) The majority of these men will present with intermediate or high risk localized cancer. While some of these men are cured, many men (20 – 40% of those diagnosed) will ultimately develop castrate resistant prostate cancer (CRPC) and succumb to the disease.[\[2\]](#) Treatment options typically involve radical prostatectomy (RP) or radiation therapy (RT) in combination with androgen deprivation therapy (ADT). Following RP upwards of 50% of patients with high-risk disease will experience a biochemical recurrence at 5 years,[\[3\]](#) and approximately 20% will die of their disease in 10-15 years.[\[4\]](#)

**Abbreviated Title:** Neoadjuvant ADT & Enzalutamide

**Version Date:** 01/25/2024

ADT interferes with androgen production or blocks androgen at the level of the androgen receptor (AR).[\[5\]](#) As a consequence prostate cancer growth is suppressed and apoptosis occurs. There is great variability in prostate cancers' sensitivity to ADT and the mechanism of induction of apoptosis when it occurs is poorly understood. Some tumors appear to exhibit primary resistance, meaning the tumor persists despite ADT. Even when cancers are initially sensitive to ADT, resistance ultimately emerges either through clonal selection or through a variety of adaptive mechanisms (secondary resistance).[\[6\]](#) Thus, the duration of long-term response to ADT is unpredictable. Due to the lack of *in vivo* markers of tumor response it has not been possible to predict either the inherent cellular properties of resistance (primary resistance) or the timing of conversion to castration resistance prostate cancer (secondary resistance).

The recent introduction of novel androgen pathway inhibitors offers an opportunity to potentially improve the cure rate of men with intermediate and high risk localized prostate cancer but has also creates a need for improved techniques to determine mechanisms of treatment response and resistance. It is this challenge that we seek to address in this clinical trial by linking pathologic tumor response to both genomics and imaging to predict androgen resistance. We will examine the response of tumors to goserelin and enzalutamide in the preoperative setting.

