## 1.20 RESPONSE CRITERIA

For the purposes of this study, patients will be monitored for response via endorectal MRI for research purposes, but there will be no formal radiographic assessment of clinical response. It is anticipated that all patients will have a stable or declining PSA throughout the study (prior to surgery) and thus additional response assessments are not required.

Index lesions identified on mpMRI will be entered into a data capture system provided by the NCI CCR.

In the rare case that patients develop a rising PSA while on this study appropriate imaging studies will be performed at the discretion of the treating physician.

Definitions:

Evaluable for toxicity: All patients will be evaluable for toxicity from the time of their first treatment with enzalutamide.

Evaluable for objective response: As described in the first paragraph above, patients will be followed for PSA and changes on endorectal MRI for research purposes only.

**Abbreviated Title:** Neoadjuvant ADT & Enzalutamide

**Version Date:** 01/25/2024

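### Post-treatment detection is part of the primary objective, but no read of the second MRI without the baseline lesion locations is planned

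*Combined protocol and SAP*

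**What the plan says.** Section numbers here follow the table of contents.

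Section 1.1.1 and Section 8 set the primary objective as the feasibility and role of mpMRI for finding and locating focal cancer, once before and once after preoperative treatment. Section 8 describes the task of the scans this way: "The imaging will be used to monitor the changes in the individual tumors located within the prostate". It plans for "50 total evaluable patients who would all undergo primary treatment and mpMRI imaging to assess the role of imaging in this setting".

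On the lesions themselves:

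- Section 2.1.1 admits only men with a prostate lesion that can be seen on MRI for biopsy. Section 3.1 allows up to 3 index lesions per man.
- Section 3.4.1 collects T2, ADC and DCE values from all foci, and PI-RADS, at both scans.
- Section 3.4.2 maps pre-treatment areas onto the post-treatment gland by deformable registration and feeds the result into the mold.
- Section 5.1.1 labels the second-scan index lesions in its table as the same ones found on the first scan. Its text speaks of identifying the foci and the earlier biopsy targets again.
- The text at Figure 4 in Section 3.1 puts making the mold first among the purposes of the second scan, and obtaining post-treatment mpMRI data second.

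On the outcome, Section 8 plans analyses of the "association with genomic traits at baseline and prostatectomy and whether there is disappearance of tumor or not" without saying whether disappearance is judged on MRI or on tissue.

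**The concern.** Detection means that a reader, given the scan, finds the cancer. Identifying a lesion again means that a reader, given the scan and the location, confirms it. The objective needs the first, while the text on lesions mostly describes the second.

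Both uses of the second scan are legitimate. Building the mold and measuring change in a lesion require the baseline locations. But if the only recorded read is made with those locations in view, the trial cannot say what mpMRI would have found after treatment on its own. That is the figure a later study of post-treatment MRI would want from this pilot, and it would probably look better than it is.

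**Working it through.** **1. The plan's own figure.** Inputs from Section 8: n = 50, probability 0.25, target at least 10 men with significant residual disease.

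P(X ≥ 10) = 1 − Σ (k = 0 to 9) C(50, k) × 0.25^k × 0.75^(50−k) = 0.8363.

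This matches the stated 83.6%. The figure holds for any class with a 25% rate, and nothing below changes it.

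**2. How many locations are known in advance.** Each man has at least one MRI-visible lesion (Section 2.1.1) and up to 3 index lesions (Section 3.1). For 50 men that is 50 × 1 = 50 to 50 × 3 = 150 index locations on record before the second scan is read. No man has none.

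**3. What is said about reading the second scan.** Sections 3.4.2 and 5.1.1 carry baseline locations forward. Section 3.4.1 is the only text that could describe an independent read, since it covers all foci and PI-RADS at both times. It names no reader, no order and no masking. No other section does.

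**4. Direction of the effect.** Let s be the chance that an unaided reader marks a baseline focus in which tumor persists. Let r be the share of foci missed unaided that are marked once the location is known. Assume that prompting does not make a reader drop a focus already found. Then

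apparent sensitivity = s + r(1 − s), so the excess is r(1 − s).

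The excess lies between 0 (r = 0) and 1 − s (r = 1). The documents give neither s nor r, so I put no number on it. It applies to foci that were baseline targets; a focus not seen at baseline gets no such help.

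**5. Where there is room for it.** Section 3.4.2 says preoperative therapy changes the MR signal of both normal and tumor tissue, and expects a large shrinkage of the gland. If that makes unaided reading harder, 1 − s is larger after treatment than before. Prompting can also lead a reader to mark a site where the tumor has gone. Section 8 expects complete disappearance in about 25% of men, or 0.25 × 50 = 12.5 men, so such sites should exist.

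**The case against.** The best defense is that the text in Section 5.1.1 is about placing tissue cores, not about reading scans. It lists focal tumors alongside earlier biopsy targets, and Section 3.4.1 covers all foci, so new lesions are not excluded. Lesion-level change cannot be measured without the baseline scan. The study is an exploratory pilot with no accuracy endpoint and no formal test.

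Much of this stands. Nothing forbids an unaided read, and one may happen in practice. It does not close the gap: detection after treatment is in the primary objective, the order of reading is unstated, and the mold work brings the baseline targets to the same scan.

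A reader might go further and infer that MRI is itself the outcome. On that reading, the objective "To determine the quantitative and qualitative mpMRI characteristics of response both before and after treatment, to predict resistance to intensive androgen targeted therapies" would test MRI against itself. Section 8 introduces its response groups straight after the sentence on imaging, and Section 6.2 says that "patients will be followed for PSA and changes on endorectal MRI for research purposes only". But Section 6.2 also says "there will be no formal radiographic assessment of clinical response". Section 1.1.2 includes the aim "To evaluate the pathological complete response rate after neoadjuvant treatment with ADT and enzalutamide", and Section 1.2 gives the purpose as "linking pathologic tumor response to both genomics and imaging to predict androgen resistance". The documents lean toward pathology and leave one term undefined; they do not plan a circular analysis.

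A reader might also infer that men without surgery would be counted, because the evaluable men are described by treatment and imaging. Section 2.1.1 requires men to be planning prostatectomy, and Sections 3.1 and 3.7 schedule it, so that is not supported either.

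**Conclusion.** The point holds as a cheap improvement to the reading procedure. As written, the plan can overstate what mpMRI detects after treatment, because every man has a known target and no read without those targets is specified. The direction rests on the assumption that knowing a location adds findings and does not remove them. The size is unknown.

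The wording of the outcome in Section 8 is a minor matter of clarity. The 83.6% is right, and its 25% is already presented as conditional. One limit should be kept in view: histology can show whether tumor is gone, but there is no whole-gland histology before treatment. It therefore cannot by itself show the minimal decline that Section 8 uses to describe the residual-disease group.

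**What to change.** In Section 3.4.1, state this order for the second MRI:

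1. Record the lesion list and PI-RADS, and lock them in the data capture system, before any baseline target is overlaid.
2. Compare that locked read with prostatectomy histology for the post-treatment detection objective.
3. Then do the registered re-read, and use it for the mold and for lesion-level change.

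In Section 8, add one sentence saying that disappearance of tumor is judged on prostatectomy histology, in line with Sections 1.1.2 and 1.2. Do not extend that sentence to the minimal-decline group, for the reason given above.

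The cost is a little extra reader time. No additional scan, biopsy or reader is needed, and the histology is already collected. The order does not remove everything: a reader may remember a case, and will know that every man entered with a visible lesion.

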### **1.2.1 Preliminary experience with ADT prior to prostatectomy**

In a previous study, the 17  $\alpha$ -hydroxylase/C17,20 lyase inhibitor abiraterone +ADT prior to prostatectomy yielded rapid PSA declines (including near or complete responses), however approximately two-thirds of studied patients demonstrated little or no tumor shrinkage.[\[7\]](#) This suggests that primary resistance to even modern anti-androgen therapy remains a formidable challenge. Several mechanisms of resistance to ADT have been identified, including persistent ligand and androgen receptor mutation.[\[6, 8\]](#) Despite this, the genomic determinants of resistance to ADT remain incompletely characterized. The extent to which such mechanisms might generalize across ADT regimens (such as ADT + Enzalutamide) or operate in specific therapeutic contexts also remains unknown.

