### **1.2.2 Rationale for Enzalutamide in the Neoadjuvant Setting**

The clinical importance of enzalutamide in the treatment of prostate cancer is likely just emerging. Given its ability to improve survival (in both chemotherapy-naïve patients and patients who have already received docetaxel), its relative lack of toxicity, and no requisite prednisone, there is increasing interest to use this treatment earlier in the disease process. One possible therapeutic strategy could employ enzalutamide in the neoadjuvant setting. It would be interesting to determine if enzalutamide can induce a complete pathologic response in some patients, or significantly shrink tumors (identified via endo-rectal MRI) in other patients. Associations with these pathologic and/or radiographic changes and delayed recurrence or cure could drive additional studies in the future with clinical endpoints.

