### 1.11.2 Registration of pre- and post-therapy prostate MRIs

Drs. [name], [name], and [name] will collaborate on evaluation and registration of pre- and post-treatment MRIs. We will use non-rigid image registration for establishing correspondence between the targets and sub-areas in the baseline and post-therapy MR images. Preoperative therapies are known to significantly alter MR signal signatures for both normal and tumor tissue. [25, 26] We expect large reduction of the prostate gland from the baseline to post-treatment imaging session. These issues undoubtedly make the registration problem very challenging. Based on the limited preliminary evidence, intensity-based deformable registration based on Mutual information similarity metric pioneered by our group [27] can be used for co-registration of pre- and post-treatment prostate MRI. Our early preliminary results show the feasibility of such registration for the data collected in preoperative therapy cases (see [Figure 5](#) below). A

variety of deformable registration methods based on Mutual Information are available in 3D Slicer, [28] and will be applied to this problem. The transformations derived by the registration will be used to map the areas in the pre-treatment scans to the post-treatment gland configuration. This information will be used in manufacturing the custom mold that will include needle access to the image-registered locations of lesions to collect tissue samples from the ex vivo specimen.

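### Does the assumed 25% rate of minimal tumor decline behind the 50-patient size conflict with the two-thirds rate quoted from an earlier neoadjuvant study?

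*Combined protocol and SAP*

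**What the plan says.** The Statistical Considerations section (Section 8 in the table of contents) anticipates three response groups. It expects that "approximately 25% of the patients will experience minimal declines in tumor and still have significant residual disease", that "25% may have complete disappearance of tumor", and that the rest improve substantially, which leaves about 50%. It wants at least 10 men in the residual-disease group for a preliminary look at genomic associations. From this it derives 50 evaluable men (ceiling 55): "if the probability of being in this category was 25%, there would be 83.6% probability of having at least 10 such patients". It then plans analyses of the "association with genomic traits at baseline and prostatectomy and whether there is disappearance of tumor or not", and labels all of this work exploratory and meant to generate hypotheses.

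The background gives one tumor-response rate from an earlier pre-prostatectomy study. In Section 1.2.1, on abiraterone plus ADT, "approximately two-thirds of studied patients demonstrated little or no tumor shrinkage", from which the protocol concludes that "primary resistance to even modern anti-androgen therapy remains a formidable challenge". Section 1.2.2 treats it as still to be seen whether treatment can "determine if enzalutamide can induce a complete pathologic response in some patients".

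**The concern.** The 25/50/25 split carries the whole sample size and has no citation. The only comparable rate in the protocol is more than twice as high for poor response, and the sizing paragraph does not mention it. If two-thirds of men showed little decline, the other two groups would share one-third. Men with disappearance would then be the smaller side of the comparison named in the closing analysis, and their number was never checked.

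The categories also lack a cut-off, a deciding modality (mpMRI or pathology) and a unit (man or lesion). Section 1.11.2 adds that "Preoperative therapies are known to significantly alter MR signal signatures for both normal and tumor tissue", which makes a purely image-based reading of disappearance less secure. At stake would be a genomic comparison with too few men on one side, and a grouping settled only after sequencing results are known.

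**Working it through.** **Inputs.** From Statistical Considerations: n = 50 evaluable, ceiling 55, target 10, rates 25/50/25. From Section 1.2.1: about 2/3 with little or no shrinkage. Assumption, not in the documents: how the other third would divide.

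**Formula.** P(X ≥ 10) = 1 − Σ C(n,k) p^k (1−p)^(n−k), summed over k = 0 to 9.

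**1. The plan's own figure.** n = 50, p = 0.25: P = 0.8363. The stated 83.6% reproduces.

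**2. The stated target at the higher rate.** n = 50, p = 2/3: 33.3 men expected, P above 0.9999. The smallest n that keeps at least 83.6% is 18 (0.8924; n = 17 gives 0.8281). The target becomes easier to meet.

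**3. The disappearance group.** At the plan's own 25% the expected number is 12.5 and P is again 0.8363. If minimal decline were 2/3, at most 1 − 2/3 = 1/3 of men remain for the other two groups:

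| Assumed division of the remaining third | Disappearance rate | Expected of 50 | P(at least 10) |
|---|---|---|---|
| All have disappearance (upper bound) | 1/3 | 16.7 | 98.7% |
| Even split | 1/6 | 8.3 | 31.7% |
| Substantial improvement to disappearance 2:1, as in 50:25 | 1/9 | 5.6 | 4.6% |

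With all 55 men evaluable, the last row becomes 7.9%.

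**4. Both extreme groups together.** At 25/50/25, the multinomial probability that both reach 10 of 50 is 0.684.

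**5. Would another main comparison help?** Minimal decline versus the rest has at least 10 men on each side with probability P(10 ≤ X ≤ 40) = 0.8363 at 25%, and 0.9873 at 2/3. Disappearance versus not has 0.8363 at 25%. At the plan's own rates the two contrasts are equal. The first is ahead only if 2/3 transfers to this regimen and the remaining third divides unfavourably.

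**6. Would more men help?** For about 80% probability of 10 men with disappearance, n would be about 74 at 1/6 and about 111 at 1/9, against a ceiling of 55. Nothing in the documents establishes either rate.

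**7. Are the two rates the same quantity?** Section 1.2.1 describes abiraterone plus ADT and limited shrinkage. The sizing paragraph describes enzalutamide plus ADT and a compound condition: minimal decline together with significant residual disease. Section 1.2.1 also says it is not known how far resistance mechanisms carry over between ADT regimens, and it names the enzalutamide combination as an example.

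**The case for a change.** The strongest case for a change is that the protocol's rationale rests on resistance being common while its sizing assumes it is uncommon, with no word to connect the two. If the sizing paragraph thinks 10 men are useful on one side of a comparison, the same standard could fairly apply to the other side. With few men there, only very large contrasts would show. If a trait occurs in 0 of 6 men with disappearance, 21 of the other 44 (48%) must carry it for a two-sided Fisher p ≤ 0.05. With 0 of 12, 11 of 38 (29%) suffice. One paragraph and a short table would cover all this without extra patients, scans or samples.

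Three facts stand: the split has no stated source, the categories are not defined, and the disappearance group was not checked. Three points limit their weight.

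- The plan sets no threshold for disappearance and proposes no Fisher test. The 10 was chosen for residual-disease men, which fits the Section 1.1.2 objective of finding predictors of primary resistance. Post-treatment sequencing under Study Design also concerns unresponsive tumor. Men with no tumor left add little to paired pre- and post-treatment sequencing, though they do count in baseline comparisons.
- Men in whom only some lesions vanish supply responding lesions for the planned within-patient comparisons, which a count of men ignores.
- The missing radiographic cut-offs are partly a declared choice, since Response Criteria states that MRI changes are followed for research without formal response assessment. The imaging and histopathology sections already collect what an analyst needs to set the groups before looking at genomic data, and the exploratory label limits what a late grouping could be used to claim.

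**Conclusion.** No stated number or rule is wrong, and the passages do not contradict each other. The 83.6% holds at its stated assumption, and the higher rate in Section 1.2.1 would raise it above 99.9%. The scarcity of men with disappearance is possible but not shown. The 4.6% needs both that the abiraterone rate transfers to enzalutamide and that the remaining third divides 2:1; without the second assumption the figure can be as high as 98.7%.

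What is missing is explanation: a basis for 25/50/25, working definitions of the response groups, and a probability for the second group. Analysts can supply these from data the trial already collects, and enrolment stays at 50 with a ceiling of 55. Putting minimal decline versus the rest ahead of the contrast the plan names would be a matter of preference, with no gain at the plan's own rates (83.6% either way). This conclusion rests on the work being a pilot whose genomic analyses are secondary and exploratory. A confirmatory comparison of men with and without disappearance would need its own sizing.
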